## 14.0 BIOSTATISTICS

This is a single-center single-arm phase II study to evaluate the efficacy and safety of benralizumab for the treatment of eosinophil-related cutaneous adverse events (ercAE) in patients having grade 2/3 ercAE to various treatments (such as checkpoint inhibitors or targeted therapies) with blood eosinophil counts of at least .3 K/mcL.

The primary endpoint of efficacy is defined as the proportion of patients who have a reduction from CTCAE grade 2/3 eosinophil-related cutaneous adverse events to grade  $\leq 1$  following treatment with benralizumab. The study will be declared positive if  $\geq 70\%$  of patients have a reduction of grade 2/3 eosinophil-related cutaneous adverse events to grade  $\leq 1$  (between Week 0/Day 1 and Week 4/Day 28).

Data from medical oncology and other MSK visits will be collected at the last study visit for each patient and immune related adverse events with grade and attribution will be included in the final analysis.

Data analysis will be conducted by externally funded biostatistician (consultant), [name] of Augmentium Pharma Consulting Inc. The Consultant will serve to review, analyze, and assess data, documents and information provided from MSK, which shall be MSK's Confidential Information, and provide subsequent guidance in a format. The Consultant will also provide independent information to support MSK's clinical research activities. Additional projects that are beyond the scope of this WP will require a separate document executed in writing between the Parties. The Services shall be provided by Consultant at the direction and discretion of MSK and all deliverables or other materials produced by the Consultant shall be subject to Section 5 of the Agreement. The consultant will have access to participant PHI including name, demographics (DOB, age, gender, race, ethnicity), medical history (treatment start and end date and treatment information) and questionnaire responses. Details of this contract are available on the PIMS regulatory binder.

#### **14.1 Populations for Analyses**

A total of 48 evaluable patients will be accrued to this study. Patients having a solid tumor or hematologic malignancy, grade 2/3 ercAE to various treatments and blood eosinophil counts of at least .3 K/mcL will be recruited from the medical oncology and dermatology clinics (Section 7.0). Patients will receive benralizumab treatment on Week 0/Day 1 and Week 4/Day 28, and will be assessed for efficacy at baseline Week 0/Day 1 (+/- 3 days), Week 2/Day 14 (+/- 3 day), Week 4/Day 28 (+/- 3day) and Week 8/Day 56 (+/- 3 days) (Section 4.2). If the second dose is missed, it will not be made up (Section 10.0). Patients can remain on study until progression of ercAE or unacceptable toxicity related to benralizumab up to 32 weeks (Section 4.2).

Patients will be considered evaluable as long as they receive at least one dose of benralizumab. Patients who are enrolled and removed from study before they receive their first dose of benralizumab will be considered inevaluable and will be replaced. Data analyses for the primary, secondary and exploratory endpoints will be based on 28 evaluable patients. Summary statistics will also be reported separately for patients removed from the study, including a summary of reasons for removal, their median duration in the study and range, mean and standard deviation of their eosinophil counts, and proportion of in ercAE categories at baseline and at all follow-up times prior to their removal from the study.

**Secondary endpoints:**

**AE-related quality of life:** Quality of life will be assessed for all patients at Week 0/ Day 1, Week 2/Day 14, Week 4/Day 28 and Week 8/Day 56, Week 16/Day 112, Week 24/Day 168, Week 32/Day 224 and 4 weeks post-last dose using PRO-CTCAE and Skindex 16 (Appendix D). Prior to conducting analyses, we will evaluate questionnaire compliance. The amount of missing data across the PRO instruments will be summarized. A questionnaire will be considered complete if enough questions were completed to be a valid score. Since these instruments are broken into sections, completion of any section for a given adverse event will be considered complete information for that adverse event. Baseline characteristics of study participants with completed and incomplete QOL data will be compared in a descriptive manner. Mouth/throat sores, dry skin and itchy skin are reported on a 5-point scale, while rash, hives and sensitivity of the skin to sunlight are reported on a 2-point scale. These symptoms will be summarized using descriptive statistics. The proportion of patients with different levels of these symptoms will be assessed at each study time point along with exact binomial confidence intervals. A summary score for the Skindex-16 will be calculated for each participant at each time point. The total Skindex-16 score will be summarized for each study time point along with 95% confidence intervals.

The Skindex-16 has been shown to have good reproducibility ( $r = 0.88-0.90$ ). Patients answer every question with a number ranging from 0 (never bothered) to 6 (always bothered). After the questionnaire is completed, the responses to each item are transformed to a linear scale of 100 that ranges from 0 (never bothered) to 100 (always bothered). Consequently, each item has a minimum score of 0 and a maximum score of 100. The Skindex-16 results are reported as an overall score and as 3 domain scores: symptoms, emotions, and functioning. For the overall score, the mean score of all items is calculated. Thus, the overall score has a minimum of 0 and a maximum of 100. Items 1 through 4 on the Skindex-16 pertain to the symptoms domain. The mean of these items is calculated, and a symptoms domain score is determined that also ranges from 0 to 100. Similarly, the emotions domain is based on items 5 through 11, and an emotions domain score is calculated on a scale from 0 to 100. The functioning domain is based on items 12 through 16, and a functioning domain score is calculated in the same manner. Skindex-16 items also are analyzed within each domain to assess the influence of specific items on the overall domain score. The means of the transformed scores for each item are compared statistically within each domain. When up to 25% of Skindex-16 items have missing responses, the items with non-missing responses will be scored. For the analysis of the Skindex-16 score change from baseline, patients with a missing score at week 4 will have the Skindex-16 score imputed by their baseline Skindex-16 score. This method is considered conservative under the

assumption that the majority of patients will withdraw prematurely from the study, resulting in missing the week 4 score.

For the PRO-CTCAE, each item is scored individually, as they are rated 0-4 by the patient. Interpretation of scores will be descriptive. If an individual item is not completed, it will be considered missing. There are otherwise no subscales or minimum thresholds for item completion to calculate a score on a given item.

**Safety and tolerability of benralizumab:** This endpoint will be measured in terms of CTCAE v5.0 ercAE. The proportion of patients with different grade categories (0, 1, 2 etc) will be assessed at each study time point along with exact binomial confidence intervals. Patients progressing to grade 4 ercAE will be removed from the study (Section 12.0). The proportion of such patients at each time point will be reported. The proportion of patients having a reduction and the proportion having an increase in ercAE grade category will be reported.

**Need for supportive medication:** The proportion of patients requiring supportive medications such as corticosteroids, antihistamines and immunosuppressants will be reported at each time point along with exact binomial confidence intervals.

**Effect of benralizumab on subsequent planned cycles of checkpoint inhibitors (CPIs) or targeted therapies:** We will measure changes in blood eosinophil levels between baseline and cycles of various planned treatments for these patients, and report the mean, standard deviation, range and number of patients scheduled to receive different therapies.

**Effect of benralizumab on corticosteroid naïve and corticosteroid dependent/refractory ercAEs:** Corticosteroid naïve patients are those not receiving corticosteroids for 14 days since Week 0/Day 1 of benralizumab treatment. Corticosteroid dependent/refractory ercAEs are patients that are on prednisone 10mg a day or greater at the initiation of study. We will report the number of corticosteroid naïve and dependent/refractory ercAE patients, measure change in blood eosinophil levels between Week 0/Day 1 and Week 8/Day 56, report descriptive statistics such as mean, standard deviation and range in these groups of patients.

**Effect on eosinophil counts:** Changes in eosinophil counts will be calculated and reported as percent reduction +/- standard deviation. In addition to comparing baseline and end-of-study percent change in eosinophils, we will also compare percent changes across baseline ercAE categories and end-of-study ercAE categories. We will use regression models to examine the association between longitudinal measurements of percent change in eosinophils at Week 0/Day 1, Week 2/Day 14, Week 4/Day 28, and Week 8/Day 56, Week 16/Day 112, Week 24/Day 168, Week 32/Day 224 and 4 weeks post-last dose and longitudinal measurements of ercAE categories.

**Body Surface Area (BSA):** Changes in BSA of ercAE will be calculated from total body photography images taken at Week 0/Day 1, Week 4/Day 28, and Week 8/Day 56. We will use regression models and descriptive statistics to quantify change in affected BSA in response to benralizumab.

**Relative Dose Intensity (RDI):** RDI of the culprit anticancer therapy will be calculated from Week 0/ Day 1 to end of study date of the trial for each patient. Relative dosage and standard dosage will be derived based on the investigators' and primary oncologists' notes and other documentation from the electronic medical records at Memorial Sloan Kettering Cancer Center. We will use regression models to assess differences in compliance to different culprit anticancer therapies in response to benralizumab.

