## 10.0 TREATMENT/INTERVENTION PLAN

- Benralizumab 30mg as a subcutaneous injection will be administered by a healthcare professional at once every 4 weeks for the first 3 doses (Week 0/Day 1, Week 4/Day 28, and Week 8/Day 56), followed by once every 8 weeks for 3 additional doses (Week 16/Day 112, Week 24/Day 168, and Week 32/Day 224), per the labeling instructions.

- Patients will also have a comprehensive physical examination at Week 0/Day 1
- Skin examination prior to benralizumab administration will be completed at Week 0/Day 1, Week 4/Day 28, Week 8/Day 56).

- Phlebotomy for CBC w differential at every visit (Screening, Week 0/Day 1, Week 2/Day 14, Week 4/Day 28, Week 8/Day 56, Week 16/Day 112, Week 24/Day 168, Week 32/Day 224, and 4 Weeks post-last dose).
- Total body photography at Screening, Week 0/Day 1, Week 4/Day 28, Week 8/Day 56,.
- Research blood collection for biomarker analysis (MSD Panel and IL-5) on Week 0/Day 1, Week 4/Day 28 and Week 8/Day 56:
  - Approximately 10 mL of blood will be collected in a green top sodium heparin Vacutainer tube. This sample will be sent to the Immune Monitoring Facility (IMF).
  - Approximately 4 mL of blood will be collected in a lavender top tube (with EDTA). This sample will be sent to Mayo Clinic.

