**Missed doses will not be made up.**

## 11.0 EVALUATION DURING TREATMENT/INTERVENTION

Study Procedures	Screening Visit (-7 days to Day 1) 	Week 0/ Day 1	Week 2/ Day 14 (+/- 3 days)	Week 4/ Day 28 (+/- 3 days)	Week 8/ Day 56 (+/- 3 days)	Week 16/ Day 112 (+/- 7 days) 	Week 24/ Day 168 (+/- 7 days) 	Week 32/ Day 224 (+/- 7 days) 	4 Weeks post-last dose (+/- 7 days)
Informed Consent	X 								
Demographics	X								
Medical history	X								
Concomitant medication review	X	X	X	X	X	X	X	X	X
Serum pregnancy test, per SOC and if applicable	X 								
Skin biopsy 	X			X					
CBC with differential	X	X	X	X	X	X	X	X	X
Comprehensive Metabolic Panel	X								
Physical exam and vital signs (HR, BP, weight, and temperature)	X								
Skin Exam (prior to Benralizumab administration)		X		X	X				
ECOG Performance Status (Appendix C)	X								
Total body photography	X	X		X	X				
Eosinophil-related Adverse Event Grading (CTCAE v5.0) (Appendix A)	X	X	X	X	X	X	X	X	X
Research blood collection for biomarker analysis (IL-5 & MSD Panel)		X		X	X				

Adverse event evaluation	X	X	X	X	X	X	X	X	X
Patient self-assessment (PRO-CTCAE (Appendix D) & Skindex 16 (Appendix B)	X	X	X	X	X	X	X	X	X
RegiSCAR Scoring System for Diagnosing DRESS Syndrome		X							
Benralizumab 30mg SC administration		X		X	X	X	X	X	

SOC, standard of care.

1. Informed consent within 45 days prior to treatment.
2. Serum pregnancy test for WOCBP within 14 days prior to treatment.
3. The baseline skin biopsy will be obtained within 30 days of treatment start, if applicable per standard of care. The biopsy at day 28 will be RNB if the patient's symptoms are improving.
4. Assessments will continue as long as the patient continues receiving benralizumab (up to 32 weeks). If a patient discontinues benralizumab, they will move to the 4 weeks post-last dose follow-up visit.
5. Screening and Week 0/Day 1 visits can be combined as long as comprehensive metabolic panel, CBC w/ differential, and pregnancy test (if applicable) are resulted to confirm eligibility prior to first benralizumab injection.

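### The visit four weeks after the last dose is summarised as one time point following Week 32, although it falls anywhere from Week 4 to Week 36 and pools early stoppers with completers

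*Combined protocol and SAP*

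**What the plan says.** Section 10.0 places the six doses at "Week 0/Day 1, Week 4/Day 28, and Week 8/Day 56" and then at "Week 16/Day 112, Week 24/Day 168, and Week 32/Day 224". In Section 11.0, footnote 4, attached to the Week 16, 24 and 32 columns, limits those assessments to patients still receiving benralizumab and adds: "If a patient discontinues benralizumab, they will move to the 4 weeks post-last dose follow-up visit". That visit has a window of plus or minus 7 days; the Week 4 and Week 8 visits have plus or minus 3 days.

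Section 14.1 (Secondary endpoints) treats the visit as one more point after Week 32. For quality of life the list of times ends "Week 32/Day 224 and 4 weeks post-last dose using PRO-CTCAE and Skindex 16", and "The total Skindex-16 score will be summarized for each study time point along with 95% confidence intervals". For ercAE grade, "The proportion of patients with different grade categories (0, 1, 2 etc) will be assessed at each study time point", with exact binomial intervals. Supportive medication is also reported by time point. The regression of eosinophil change on ercAE category lists the visit as one of its longitudinal times. No rule splits the visit by last dose or maps it to actual study week, and no denominator or fixed cohort is set for the by-visit summaries.

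**The concern.** The other columns are fixed in time since first dose. This one is fixed in time since last dose, so under a single label it combines patients seen after one injection with patients seen after six. It also directly follows three columns restricted to patients still on treatment. Stopping is linked to outcome, because Sections 1.0, 4.2 and 14.1 allow patients to remain only until ercAE progression or unacceptable toxicity.

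A reader of the finished table would naturally compare the last two columns to judge whether control holds after the final injection. As planned, that comparison cannot separate real change from a change in who is counted. The regression has a related problem: one nominal time is given to observations that may be up to 32 weeks apart (Week 4 against Week 36).

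**Working it through.** The plan's own figure. The only stated design figure is power above 80% for the primary test (Section 14.1). With 28 patients, a rule of 17 or more responders, 40% under the null and 70% expected, exact binomial calculation gives a type I error of 0.0215 and power of 0.897, which agrees. That test uses Week 0 to Week 4 and does not depend on this point.

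Step 1: when the visit falls. Visit week = last-dose week + 4. Last doses at Weeks 0, 4, 8, 16, 24 and 32 give Weeks 4, 8, 12, 20, 28 and 36, or Weeks 3 to 37 with the window. If footnote 4 is read as applying only from the columns that carry it, patients have had at least three doses and the visit still spans Weeks 12 to 36.

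Step 2: a no-relapse model. The documents give no stopping rates, so these are assumptions. Let R be the proportion at grade 1 or below at Week 4. Nobody changes grade afterwards. In each of the four intervals from Week 4 to Week 32, a fraction a of responders and b of non-responders stop. All treated patients attend the post-last-dose visit.

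- Week 32 column: R(1−a)^4 / [R(1−a)^4 + (1−R)(1−b)^4]
- Post-last-dose column: R

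For R = 0.70, a = 0.05, b = 0.25: 0.70 × 0.8145 = 0.5702 and 0.30 × 0.3164 = 0.0949, so Week 32 = 0.5702 / 0.6651 = 85.7%. The next column reads 70.0%.

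| R | a (responders) | b (non-responders) | Week 32 | Post-last-dose | Apparent change (points) |
|---|---|---|---|---|---|
| 70% | 5% | 25% | 85.7% | 70.0% | −15.7 |
| 70% | 5% | 50% | 96.8% | 70.0% | −26.8 |
| 70% | 10% | 10% | 70.0% | 70.0% | 0 |
| 70% | 25% | 5% | 47.5% | 70.0% | +22.5 |
| 40% | 5% | 25% | 63.2% | 40.0% | −23.2 |

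Step 3: attendance. In the second row, if only half of non-responders attend, the final column reads 0.70 / (0.70 + 0.15) = 82.4%. With a quarter attending it reads 0.70 / (0.70 + 0.075) = 90.3%. With none it reads 100% and the fall disappears.

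Step 4: Skindex-16. Assume means of 20 in responders and 60 in non-responders. With the first row's stopping rates, Week 32 = (0.5702 × 20 + 0.0949 × 60) / 0.6651 = 25.7. The final column is 0.70 × 20 + 0.30 × 60 = 32.0. The mean worsens by 6.3 points although no patient has changed.

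Step 5: same patients throughout. If the same treated patients form the denominator at every point, the no-relapse series is flat at R and the artefact is zero.

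**The case against.** A reader might infer that the series is bound to show a relapse even when nobody relapses. The documents do not support that. They give no stopping rate by response and do not require a non-responder without progression to stop. Equal stopping gives no fall, and earlier stopping by responders gives a rise. Attendance by the worst cases is also uncertain: Section 13.2 removes patients who progress and are placed on other agents, Section 14.1 removes those reaching grade 4, and footnote 4 does not say that removed patients return.

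A range of 8 to 45 points is equally tempting. It follows from fixing completers at 90%, early stoppers at 20% to 50% of patients, and 0% to 50% of stoppers at grade 1 or below: 0.20 × (0.90 − 0.50) = 0.08 and 0.50 × (0.90 − 0) = 0.45. Those inputs settle the sign in advance. The fall also comes from selection in the Week 32 column: with everyone in that denominator, both columns would agree.

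Three further objections have weight:

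- The visit does have a definition, four weeks after the last dose, and the label says so. The plan names no endpoint comparing it with Week 32, and these summaries are descriptive.
- The visit-week arithmetic is nominal. If dosing ends at the Week 16 visit after a last dose at Week 8, the Week 12 window has already passed, so the assessment would be late or missed.
- Because footnote 4 is not attached to the Week 4 and Week 8 columns, it is only one reading that a patient stopping after dose 1 or 2 loses the regular visit.

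Section 14.1 also promises a separate summary of removed patients, but their ercAE categories are given only at times before removal. It does not describe this visit or take those patients out of the pooled column. What stands is that one column combines several study weeks and follows columns with a different, selected membership.

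**Conclusion.** The point holds as a defect in how the secondary summaries and the regression handle time. The post-last-dose visit spans nominal Weeks 4 to 36 (12 to 36 on the narrower reading) and is listed as one time point after Week 32, so a difference from Week 32 can arise from composition alone. A spurious fall is likely if patients with worse skin stop earlier and attend, which the progression rule makes plausible, but neither its presence nor its direction is established. The figure of about 16 points rests on 70% response, no relapse, full attendance, and assumed stopping of 5% of responders and 25% of non-responders per interval; other assumptions give zero or a rise. The primary Week 4 test and its power are unaffected. This is a worthwhile, inexpensive correction and not a threat to the main conclusion.

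**What to change.** In the analysis text and table shells:

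- Keep this visit off the week-indexed series.
- Report Week 36 only for patients who received dose 6, as a paired change from their own Week 32 value.
- Tabulate early stoppers' visits separately by number of doses received, with actual study week and reason for stopping.
- If such an assessment falls in the Week 4 or Week 8 window, analyse it as that visit.
- Show the number contributing to every column.
- In the eosinophil and ercAE regression, use actual time since first dose with an off-treatment indicator.

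The cost is wording and table layout, with no new data. The downside is smaller numbers, and so wider intervals, in the post-dose columns.

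### The Skindex-16 missing-item rule sets no minimum per domain, so an overall score can stand with no symptom item and a domain score can rest on one item

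*Combined protocol and SAP*

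**What the plan says.** The scoring rules are in Section 14.1, Secondary endpoints, under AE-related quality of life.

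- Scores reported: "The Skindex-16 results are reported as an overall score and as 3 domain scores: symptoms, emotions, and functioning".
- Item range after rescaling: "each item has a minimum score of 0 and a maximum score of 100".
- Overall score: "For the overall score, the mean score of all items is calculated".
- Domain make-up: "Items 1 through 4 on the Skindex-16 pertain to the symptoms domain"; "the emotions domain is based on items 5 through 11"; "The functioning domain is based on items 12 through 16". Each domain score is the mean of its items.
- Missing items: "When up to 25% of Skindex-16 items have missing responses, the items with non-missing responses will be scored".
- Completeness: "A questionnaire will be considered complete if enough questions were completed to be a valid score". What makes a score valid is not defined, either overall or by domain.

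The same section replaces a missing week 4 score by the patient's baseline score in the change-from-baseline analysis. It summarizes the total score at each time point with a 95% confidence interval. For the PRO-CTCAE it states outright that there are no subscales and no minimum number of items. The Skindex-16 does have subscales, but the plan gives no minimum for them.

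**The concern.** A limit set on the whole questionnaire does not protect a short subscale. The permitted number of blanks equals the length of the symptoms domain, which in a trial of rash, itch and urticaria is the domain closest to the treated event. A questionnaire with that block empty still yields an overall score, made up of emotions and functioning only. That score is then summarized and compared with scores that do contain the symptom items.

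If a patient leaves different items blank at Day 1 and at a later visit, the two scores measure different mixtures of items, and part of the difference between them may be a scoring artefact. The trial has a single arm, so no control group would show or offset it. The week 4 baseline imputation does not act here, because the overall score counts as present. A domain score from one item is also noisier than one from the full set, and the plan does not say whether it should be reported.

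**Working it through.** The plan states no standard deviation, effect size or expected missing-item rate for the Skindex-16, so there is no figure of its own to reproduce. The inputs from Section 14.1 are the 25% limit, the 16 items and the domain sizes of 4 (items 1 to 4), 7 (items 5 to 11) and 5 (items 12 to 16). Item levels and rates of blanks below are assumptions and are marked as such.

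**1. Permitted blanks.** 0.25 × 16 = 4 items, anywhere in the questionnaire.

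**2. Fewest answered items per domain, max(0, k − 4).**
- Symptoms: 4 − 4 = 0. With 3 blank (3/16 = 18.75% of the questionnaire), the domain is scored from 1 item.
- Functioning: 5 − 4 = 1, so 80% of the domain is missing.
- Emotions: 7 − 4 = 3, so 57% of the domain is missing.

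**3. How many patterns this covers.** Patterns with 0 to 4 blanks: 1 + 16 + 120 + 560 + 1,820 = 2,517. Patterns with at most one blank in each domain: (1 + 4) × (1 + 7) × (1 + 5) = 240. The other 2,517 − 240 = 2,277 accepted patterns leave at least one domain with more than 25% of its items missing. These are counts of possible patterns and do not say how often each will occur.

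**4. Overall score with items 1 to 4 blank.** Let S be the mean of the symptom items and O the mean of the other 12.
- Full score: (4S + 12O)/16. Score as computed under the rule: O.
- Shift: O − (4S + 12O)/16 = 0.25 × (O − S).

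For assumed levels:
- S = 60, O = 60: shift 0.
- S = 60, O = 40: 45 becomes 40, shift −5.
- S = 70, O = 40: (280 + 480)/16 = 47.5 becomes 480/12 = 40.0, shift −7.5.
- S = 80, O = 40: 50 becomes 40, shift −10.
- Limits: −25 (S = 100, O = 0) and +25 (S = 0, O = 100).

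**5. Largest possible shift in a domain score, 100 × (1 − answered/k).** Symptoms from 1 of 4: 75 points. Functioning from 1 of 5: 80 points. Emotions from 3 of 7: 57 points. These are bounds, not expected values.

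**6. Noise of a one-item score.** With equal item variances and an assumed inter-item correlation r, the SD of one item relative to that of a four-item mean is 1/√((1 + 3r)/4). This is about 1.5 at r = 0.3 and about 1.1 at r = 0.7.

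**7. Group mean of the overall score.** If a fraction f of patients leave the symptom block blank at one visit only, the mean moves by f × 0.25 × |O − S|. For assumed f of 5% to 20% and a gap of 10 to 40 points, this runs from 0.05 × 0.25 × 10 = 0.125 to 0.20 × 0.25 × 40 = 2.0 points.

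**The case against.** The strongest reply is that the rule only permits a distortion and does not produce one. Three things must coincide: blanks clustered in one domain, blank items that would have averaged differently from the answered ones, and a pattern that differs between visits. If S equals O the shift is zero. This stands, and it limits the point to scores that can shift.

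A reader might infer that the rule favours benralizumab. The documents do not support that. With S above O, symptoms left blank at the later visit make the patient look better, but the same blanks at Day 1 make the patient look worse. Nothing in the plan says which is more likely.

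A reader might also infer that one-item domain scores enter confidence intervals with full weight. The plan specifies 95% intervals for the total score only. It says that domain scores are reported but gives no interval or weighting for them.

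The wording is also less settled than a strict reading suggests. The rule follows sentences on analysis within domains and does not say which score it governs. Applying it to all 16 items is the literal reading; the safe description is that no limit by domain is stated. If all four symptom items are blank, no symptoms score can be computed, so the gap would show in the domain results.

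Finally, the plan checks questionnaire compliance before analysis, summarizes missing PRO data, compares patients with complete and incomplete data, and looks at single items. These steps would probably reveal a cluster of blank symptom items. They do not supply a scoring rule for it.

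**Conclusion.** The point holds as a gap in the scoring rule. The plan limits blanks only across the questionnaire and states no minimum per domain. The literal rule therefore accepts an overall score with no symptom item, a symptoms or functioning score from one item, and an emotions score from three. That part follows from the plan's own numbers and needs no assumption.

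The consequence is conditional. For one patient the overall score can move by 0.25 × (O − S), which is 7.5 points at the assumed 70 and 40, and a domain score can move by more. For the group mean, the 0.1 to 2 points rest on assumed rates of blanks and assumed gaps. The documents give neither, so the actual effect cannot be estimated and is probably small.

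The endpoint is secondary and mostly descriptive, with no success threshold. The primary endpoint is based on CTCAE grade and is not affected. This is a minor correction, worth making because it is cheap and best settled before scoring.

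**What to change.** Replace the single rule in Section 14.1 with three statements.

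1. **Domain scores.** Report a domain score only when no more than 25% of that domain's items are missing. This allows 1 blank of 4 for symptoms (0.25 × 4 = 1), 1 of 7 for emotions (1.75, rounded down) and 1 of 5 for functioning (1.25, rounded down).
2. **Overall score.** Keep the 25% limit across the 16 items, but fill each blank with the patient's mean of the answered items in the same domain at that visit. Do not compute the overall score if a domain is entirely blank.
3. **Week 4 imputation.** State that the baseline score does not replace a domain score that is unscorable only because of blank items on a returned questionnaire, nor an overall score left uncomputed because a domain is blank. Leave these missing and count them.

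The filling step keeps each domain's weight in the overall score. At the assumed 70 and 40 with three symptom items blank, the mean of the answered items is (70 + 12 × 40)/13 = 42.3. Filling from the one answered symptom item gives (4 × 70 + 12 × 40)/16 = 47.5, the full-data value, provided that item sits at the domain mean.

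A simpler rule, voiding the overall score whenever any domain exceeds 25% missing, would be worse under the current imputation. Of the 120 two-blank patterns, 6 + 21 + 10 = 37 put both blanks in one domain. A patient with 14 of 16 items answered at week 4 could then lose the overall score and be set to zero change. For an assumed true change of −30, that is a 30-point error.

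The cost is a few sentences and no new data. A few more domain scores become missing. Within the 4-blank limit, only the symptoms domain can be entirely blank, so the overall score is lost in just 1 of the 2,517 accepted patterns.
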